	9	6-26 weeks	Fever (>38°C) - 1 Diarrhoea- 1	0 0	Serum antibody rise to vaccinees 2, placebo 0	
	42	6-26 weeks	Fever (>38°C) - 4 Diarrhoea- 2	5 1	Serum antibody rise to vaccinees 19, placebo 0	

SB Biologicals has acquired the strain and taken over the manufacturing process and clinical development of the 89-12 vaccine from AVANT and has implemented several process changes and prepared a lyophilized HRV vaccine based on a cloned P43 89-12 HRV strain (referred to as RIX4414).

It is known that the same vaccine can achieve different levels of immune response and efficacy in different study populations, and therefore it is important to test the study vaccine in different geographic settings. GSK Biologicals is therefore commencing trials in Asia, Latin-America and Africa to begin testing of its HRV vaccine's effectiveness in preventing gastroenteritis.

The aim of this dose-ranging study is to identify the most suitable dose and regimen of the vaccine for Bangladesh infants and to determine if there is a difference in immune responses between the two viral concentrations using two different schedules. The rationale for the use of several doses and several viral concentrations is four fold: First, to implement rotavirus vaccination as part of the existing EPI schedule, infants should be vaccinated at a very early age (6-8 weeks old) and with a short interval between doses. At this young age, infants are expected to have considerable levels of circulating maternal antibodies. The importance of maternally acquired anti-rotavirus specific antibodies has been evaluated in several clinical trials performed in infant-mother pairs. As expected, the presence of maternally acquired antibodies was shown to interfere with live attenuated oral rotavirus vaccine in infants (Pickering et al, 1995). The administration of an additional dose might overcome the potential interference of maternal antibodies. Therefore, the immunogenicity of GSK Biologicals' HRV vaccine needs to be evaluated at two and at three doses.

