In study part 1, the safety in toddlers will be assessed in a small number of subjects. The purpose of this study is to assess the safety and reactogenicity of the proposed doses of the candidate vaccine when administered orally in a small number of toddlers before clinical development continues in the target population, infants. The safety data collected during the fifteen-day follow-up period (day 0 to day 14) will be reviewed by the medical monitor without breaking the study blind. If there are no safety concerns during this blinded review of the safety data collected, participants in the study part 2 will be vaccinated with the viral concentration of the proposed doses.

Toddlers (2-4 years old) Recruitment, consent, and randomization (1:1:1) with 30 subjects in $10^{5.0}$ ffu (1 dose), 30 subjects in $10^{6.0}$ ffu (1 dose) and 30 in placebo group.	One dose of vaccine or placebo, with surveillance for adverse events (by home visits) and fecal excretion of virus
---	--

Part 2 (Double-blind safety and immunogenicity assessment in infants)

In study part 2, the safety and immunogenicity of the candidate vaccine will be assessed in the target age group - infants approximately 6 weeks of age. Escalating doses (viral concentrations of 10^5 ffu and 10^6 ffu) will be evaluated. All infants will receive by co-administration the recommended EPI vaccines at 6-10-14 weeks, including OPV.

Infants (6-14 weeks old) Recruitment, consent, and randomization (2:2:2:1) with 136 subjects in $10^{5.0}$ ffu (2 doses), 136 subjects in $10^{5.0}$ ffu (3 doses), 136 subjects in $10^{6.0}$ ffu (2 doses) and 68 in placebo group.
	
Two/three doses of vaccine or placebo, 4 weeks apart, with surveillance for adverse events (by home visits) and blood sampling at each study visit for antibody titer changes. Fecal excretion of virus in the first 150 enrolled subjects.

---	---

The investigator and his staff will be aware of the possible increased risk of intussusception and will consider this diagnosis among children presenting symptoms of intussusception. Symptoms consistent with intussusception are severe colicky abdominal pain, persistent vomiting, bloody stools, abdominal bloating and fever up to 41°C. The investigator and his staff will take appropriate actions to evaluate and treat the condition.

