- Serum specimens will be collected at each study visit and 4 weeks after the last dose from all subjects only in part 2.
- Data collection will be by conventional paper case report forms (CRF's).

Sample size considerations

During the first phase of the study (immunization of children 2-4 years of age), the outcome of interest is reactogenicity. Even if intussusception were to occur with a relative risk similar to that observed with RRV-TV, we do not expect to observe intussusception with the small numbers included in this Phase I study. We will however use fever as a measure of reactogenicity. Based on previous studies in the USA involving active surveillance, we expect a background rate of 5% of fever (among placebo recipients). With 90 subjects (30 with $10^{5.0}$ ffu, 30 with $10^{6.0}$ ffu and 30 placebo), we will have 80% power ($p=0.05$) to detect a 35% incidence of fever among vaccinated subjects (assuming a background rate of 5% among controls). The same sample size assumptions hold true for the infant study.

For the second part involving both safety and immunogenicity, the primary outcome measure of interest is immunogenicity, although through this and all subsequent studies, reactogenicity will continue to be monitored. With 136 vaccinees in each vaccine group ($10^{5.0}$ 2 doses, $10^{5.0}$ 3 dose, $10^{6.0}$ ffu 2 doses) and 68 subjects receiving placebo, we will be able to detect a difference in take rates of 15% between the two dose levels (70% vs. 85%). The sample size will be sufficient to detect a difference in take rates of 12% (75% vs. 87%) between 2 doses of $10^{5.0}$ ffu and $10^{6.0}$ ffu. We are also assuming that 35% of infants will be exposed to wild type rotavirus during the 8 week study period and our numbers will be sufficient to differentiate a take rate between vaccine responses and background responses. If the proportion among controls is actually lower, and 70% of children have a four-fold rise in serum antibody titer, then the number of subjects required to achieve significance will be lower.

Study Cohort

Numbers of subjects / centres: Field workers will identify children of appropriate age, inform families of the purpose and scope of the study and offer participation. It is planned to vaccinate 10-12 children daily, and first dose of vaccines are expected to be complete within 2 weeks of the start of the study.

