- On day 42, insure that all concomitant medication taken during the study have been recorded.

Day 43 to 6 months.

- Monthly active surveillance to complete 6 months of followup. With each visit, inquire about symptoms or illnesses among subjects.
- At end of 6 months, terminate subject from the study

For infants(Part 2)

Day 0 (Visit 1)

- Same procedures as performed for toddlers in part 1.
- Obtain a blood sample for serology
- Prepare study vaccine and administer dose 1
- Collection of stool sample for rotavirus antigen by ELISA

Day 3, 7, 14, and 21 (first 150 subjects only)

- Collection of stool sample for rotavirus antigen by ELISA

Day 1-day 27

- Carry out active surveillance with all subjects by visiting house daily for 2 weeks and thereafter twice weekly. Measure rectal temperature daily. Use daily form to record symptoms or lack of symptoms. Have physician available at clinic and inform family of subjects that the physician is available should there be any illness during the time of the study. If subjects are brought to the clinic, record all symptoms in patient medical records. These medical records will be the source documents for the passive surveillance.

Day 28

- Insure that subject is eligible for dose 2 according to inclusion and exclusion criteria
- Obtain a serum blood sample for serology
- Prepare study vaccine and administer dose 2
- Collection of stool sample from subjects (first 150 only) for rotavirus antigen by ELISA

Day 29 – day 42

- Carry out active surveillance with all subjects by visiting house daily for 2 weeks. Measure rectal temperature daily. Use daily form to record symptoms or lack of symptoms. Have physician available at clinic and inform family of subjects that the physician is available should there be any illness during the time of the study. If subjects are brought to the clinic, record all symptoms in patient medical records. These medical records will be the source documents for the passive surveillance.

Day 31, 35, 42, 49 (first 150 subjects only)

- Collection of stool sample for rotavirus antigen by ELISA

Day 43-day 55

- Twice weekly active surveillance inquiring about symptoms or illnesses among subjects.

Day 56

- Insure that subject is eligible for dose 3 according to inclusion and exclusion criteria

- Obtain a serum blood sample for serology
 - Prepare study vaccine and administer dose 3
 - Collection of stool sample from subjects (first 150) for rotavirus antigen by ELISA
- Day 57-day 70

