Baseline characteristics of the subjects receiving vaccine and placebo will be examined for group comparability. Any significant baseline differences will be controlled for during data analysis. The frequency distribution will be examined to assess the distribution of data. Proportion of infants with adverse events will be compared between the different groups (vaccine, placebo, different doses and viral concentrations). Proportion of subjects that shed rotavirus at different time periods will be compared. Serological measures (proportion with ≥ 4 -fold increase in titer and geometric mean titer) will be compared between different viral concentrations/ doses and placebo recipients.

The proportions will be compared using χ^2 -tests and rate ratios (95% confidence intervals). The geometric mean titers (GMT) will be compared using non-parametric tests. Multivariate analysis will be done to simultaneously adjust for different factors.

Ethical Assurance for Protection of Human Rights

Describe in the space provided the justifications for conducting this research in human subjects. If the study needs observations on sick individuals, provide sufficient reasons for using them. Indicate how subject's rights are protected and if there is any benefit or risk to each subject of the study.

Human rotavirus vaccine (RIX4414), designed for preventing rotavirus will be evaluated among young children since the risk of the disease is greatest in that age group. Infants will be enrolled after their parents have been given a full explanation of the study and they have understood the implications of participating in this study, and have agreed to participate in writing. The study will be conducted according to Good Clinical Practices, the Declaration of Helsinki, and local rules and regulations of Bangladesh and the ICDDR,B.

The investigator and his staff will be aware of the possible increased risk of intussusception and will consider this diagnosis among children presenting symptoms of intussusception. The investigator and his staff will take appropriate actions to evaluate and treat the condition. A child with suspected intussusception will be referred to a local hospital in Dhaka (Children's hospital, Shishu Hospital). The hospital has the experience and capacity for diagnosis, non-surgical and surgical management of intussusception, and a pediatric surgeon at this hospital is a co-investigator on the protocol to assume

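### The 2-versus-3-dose contrast of 10^5 ffu does not name the Day 56 response; if both arms are treated alike until that serum, the unstratified test is valid but gives up power that the planned samples could supply

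*Protocol*

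**What the plan says.** The Background section says why a third dose is studied: "The administration of an additional dose might overcome the potential interference of maternal antibodies". That sentence is rationale and describes no test.

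The analysis is fixed in Data Analysis. The proportion with at least a 4-fold rise and the geometric mean titre "will be compared between different viral concentrations/ doses and placebo recipients". Proportions are compared by chi-square tests and rate ratios, and titres by non-parametric tests. The section adds that significant baseline differences will be controlled for and that a multivariate analysis will adjust for different factors, which it does not name. It gives no reading time.

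On sampling, Outline of the study states: "Serum specimens will be collected at each study visit and 4 weeks after the last dose from all subjects only in part 2". The Part 2 procedures place serum at Days 0, 28, 56 and 84. At Day 56 they list, in order, "Insure that subject is eligible for dose 3 according to inclusion and exclusion criteria", the blood sample, then dose 3. One visit schedule serves all infants. It does not say which visit is placebo in the 2-dose arms.

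Sample size considerations plans "With 136 vaccinees in each vaccine group" and treats the arms as independent proportions.

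**The concern.** The third dose is meant to help infants in whom two doses have not taken. By the protocol's own planning figures, 70-75% of infants would already have responded by Day 56. If both 10^5 arms have had the same treatment by then, any difference between them in that response is chance. An unstratified comparison of final proportions still carries it in full.

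A third-dose effect of moderate size could therefore be missed, or estimated less precisely than the collected sera allow. The Response to external Reviewers' comments says that this trial will inform the choice of viral concentration and dose regimen for phase III, so the precision of this contrast matters.

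**Working it through.** **Inputs from the protocol.** n = 136 per arm, with equal allocation to the two 10^5 arms (Sample size considerations). Take after two doses T = 70% (the lower rate in the first planning pair) or 75% (the lower rate in the second pair, and the earlier vaccine result cited in the Response to external Reviewers' comments). Wild-type exposure is 35% in 8 weeks.

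**Assumptions.** The 2-dose arm is vaccinated at Days 0 and 28. Both arms are read at Day 84. The wild-type rate is constant and every exposure counts as a conversion. There is no dropout. The third dose converts a fraction q = 0.40 of non-responders; this value has no source in the documents. Tests are two-sided at 5%.

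**The plan's own figures.** For 70% vs 85%, 80% power needs 121 per arm, or 134 with continuity correction, so 136 is reproduced; power at 136 is 84.6%. For 75% vs 87%, power at 136 is 71.5%. The protocol states no power for Part 2 take rates. The only pair it labels explicitly is 10^5 against 10^6 at two doses; none is labelled as 2 versus 3 doses.

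**Conversion over Days 56-84 among Day 56 non-responders.**
- 2-dose arm: b = 1 - sqrt(0.65) = 0.194.
- 3-dose arm: c = 1 - (1 - q)(1 - b) = 1 - 0.60 × 0.806 = 0.516.
- Gain in take = (1 - T)(c - b): 0.25 × 0.3225 = 8.1 points at T = 75%, and 0.30 × 0.3225 = 9.7 points at T = 70%.

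**Check by hand at T = 75%.** Final take is 0.75 + 0.25 × 0.194 = 0.798 against 0.75 + 0.25 × 0.516 = 0.879.
- Unstratified SE = sqrt[(0.798 × 0.202 + 0.879 × 0.121)/136] = 4.4 points. Then 8.1/4.4 - 1.96 is about -0.1, so power is about 44%.
- Stratified: without waning only the roughly 34 non-responders per arm contribute. SE = 0.25 × sqrt[(0.194 × 0.806 + 0.516 × 0.484)/34] = 2.7 points, or 2.9 in simulation, where the stratum sizes vary. With 2.9, power is about 80%.

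**Simulation** (40,000 trials per row; chi-square against Cochran-Mantel-Haenszel stratified by Day 56 response; q = 0.40). Waning is the fraction of Day 56 responders below 4-fold at Day 84, equal in both arms.

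| Waning | T = 75%: unstratified / stratified | T = 70%: unstratified / stratified |
|---|---|---|
| 0 | 44% / 80% | 53% / 87% |
| 5% | 39% / 59% | 48% / 71% |
| 10% | 35% / 47% | 44% / 59% |

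With q = 0 both tests reject in about 5% of trials.

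**Dependence on the size of the gain** (no waning, b = 0.194).

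| Gain | T = 75% | T = 70% |
|---|---|---|
| 5 points | 19% / 44% | 17% / 39% |
| 8 points | 44% / 80% | 38% / 74% |
| 12 points | 83% / 99% | 74% / 97% |
| 15 points | 97% / 100% | 93% / 100% |

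A 12-point gain would need the third dose to convert about 60% (T = 75%) or 50% (T = 70%) of non-responders. A 15-point gain would need 74% or 62%.

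**If the dosing-order assumption fails.** Suppose the 2-dose arm has a placebo visit before Day 56, so that only 50% have responded at Day 56 against 75% in the 3-dose arm (50% is assumed), and both finish at 79.8%. There is then no difference to find. The chi-square rejects in 5% of trials and the stratified test in 98%.

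**The case against.** **The chi-square test on randomised arms is valid, and strata and covariates are usually settled in the analysis plan.** The first part stands: this is lost efficiency, not an error. The second stands in part. The analysis plan is not shown and may name Day 56 status. But the protocol does fix a method for this contrast, and a better one is available from samples it already collects.

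**Multivariate adjustment is promised.** This stands as a limit. A reader might infer that the plan tests only raw proportions and never uses Day 56 status. The text does not support that, because the factors are left open. What can be said is that Day 56 status is not named.

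**The dosing order in the 2-dose arm is not written.** This stands and makes the recommendation conditional. A reader might take stratifying on Day 56 response to be free of bias in any case; the last check above shows that it is not.

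**The loss depends on assumptions.** This stands. A reader might infer that power is cut in half. That roughly fits gains of 5 to 8 points without waning, and the protocol states no such gain. At 12 points the loss is about 16 points of power (T = 75%) to 23 (T = 70%), and at 15 points about 3 to 7. With 10% waning it is about 12 to 15 points at q = 0.40.

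**Responders can still inform the titre comparison.** This stands: a third dose may raise titres in infants who have already responded. The argument about non-responders applies to the 4-fold endpoint only.

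**Conclusion.** The point holds as a conditional efficiency gain. If the 2-dose 10^5 arm is vaccinated at Days 0 and 28, the named 2-versus-3-dose comparison carries avoidable chance variation from the first two doses. At 136 per arm and q = 0.40, power is 44-53% unstratified against 80-87% stratified without waning, and 35-48% against 47-71% with 5-10% waning. The benefit is largest for modest third-dose effects and small at a gain of 15 points.

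The size rests on the assumed q, the constant wild-type rate, no dropout and a common Day 84 reading. The documents do not show an invalid test, a general halving of power, or a plan that excludes Day 56 status.

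**What to change.** 1. State which visit is placebo in the 2-dose arms, so that it is clear whether both 10^5 arms are treated alike up to the Day 56 serum. Settle this first.
2. In Data Analysis, name Day 84 as the reading time for both 10^5 arms. If serum 4 weeks after the last dose were read as Day 56 in one arm and Day 84 in the other, wild-type conversion alone would add about 0.25 × 0.194 = 4.8 to 0.30 × 0.194 = 5.8 points to the 3-dose arm.
3. Provided the arms are treated alike until the Day 56 serum, make the 2-versus-3-dose contrast a Mantel-Haenszel test and risk difference stratified by 4-fold response at Day 56. Report Day 56-84 conversion among Day 56 non-responders by arm.
4. Under the same condition, model log Day 84 titre on arm and log Day 56 titre, in all infants.
5. Keep the raw proportions as description.
6. If the 2-dose arm has its placebo visit before Day 56, do not stratify on or adjust for Day 56 status; keep the unstratified comparison.

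The cost is wording only. The Day 56 and Day 84 sera are already planned in all Part 2 infants.

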- Carry out active surveillance with all subjects by visiting house daily for 2 weeks. Measure rectal temperature daily. Use daily form to record symptoms or lack of symptoms. Have physician available at clinic and inform family of subjects that the physician is available should there be any illness during the time of the study. If subjects are brought to the clinic, record all symptoms in patient medical records. These medical records will be the source documents for the passive surveillance.

Day 59, 63, 70, 77 (first 150 subjects only)

- Collection of stool sample for rotavirus antigen by ELISA

Day 71- 83

- Twice weekly active surveillance inquiring about symptoms or illnesses among subjects.

Day 84

- Obtain a serum blood sample for serology.
- Insure that all concomitant medication taken during the study have been recorded.

Day 85 to 6 months after third dose

- Monthly active surveillance to complete 6 months of follow up. With each visit, inquire about symptoms or illnesses among subjects.
- At end of 6 months, terminate subject from the study

Laboratory testing

Fecal samples will be collected as whole stool samples by the parent of the subject or the field worker using a stool cup and taken to the field clinic within 8 hours of passing of the sample. At the clinic, it will be placed in a glass vial with saline (about 10% feces to saline ratio), labelled and placed into a refrigerator (+4°C). Specimens will be transported to the ICDDR,B virology lab within 48 hours and maintained at +4° C until tested. Blood specimens will be obtained by venipuncture (about 3 ml) in clinic using sterile technique. Blood will be placed into a vacutainer without anticoagulants. After blood has clotted, it will be centrifuged and serum transferred to three labelled cryovials (3 aliquots) and frozen at -20° C.

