TRAVEL COSTS						
International travel						20,000
Investigator Meeting						5,000
Local transportation cost						5,000
SUB-TOTAL:						30,000
SUPPLIES & OTHER COSTS						
Office rent, communications and utilities						10,000
Mobile phone						1,500
Drugs						1,000
Office & field supplies						1,500
Printing & Publications of forms						10,000
Spoon, cups, cylinder etc.						750
Needles, Syringes, thermometers, etc.						8,000
Furniture						1,500
Cold pack						100
Lab supplies cost						4,000
Shipping cost for sending specimen						10,000
Cost for safety monitoring Comm						1,000
Cold box (4)						250
Publications						500
Hospitalization/Attend cost (Shishu Hospital)						2,050
Service charges (Shishu Hospital)						
- [name]			15	5%	100	1,500
- Medical Officer			15	15%	30	450
SUB-TOTAL:						54,100
INTER-DEPARTMENTAL SERVICES						
Repair & maintenance						500
Transport (land)						4,000
Specimen handling fees						5,000
IgA ELISA@4X3X525	4	4	576			9,216
RV [contact]	3.3	1	2430			8,019
Culture RV						5,000
Typing RV (G/P/Electropherotyping)						6,000
Medical Illustration						500
Mimeography, Library charge etc.						500
SUB-TOTAL:						38,735
CAPITAL ITEMS						
Computers (2)/printer/UPS/accessories etc.						5,000
Gel electrophoresis apparatus						3,000
Refrigerator (1)						1,000
Freezer						6,000
SUB-TOTAL						15,000
TOTAL DIRECT COSTS:						319,870
OVERHEAD @25%						79,968
TOTAL PROJECT COSTS:						399,838

[name] 31.5.24
[name]
 Senior Budget & Cost Officer
 ICDDR, B, [name]
 [name], Bangladesh.

Budget Justifications

Please provide one page statement justifying the budgeted amount for each major item. Justify use of man power, major equipment, and laboratory services.

Budget justification

Briefly relate each item in the budget (personnel, supplies, equipment, animals, patient costs, travel, etc.) to the activities outlined in the research proposal

The total duration of the proposed study will be of 15 months. The study involves recruitment of study subjects, either one or two or three doses of vaccination to about 566 healthy children (toddlers and infants), follow up at their homes and collection of blood and stool specimens.

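### The single infant schedule lists a dose 3 for every child although two of the arms are 2-dose arms, and the 8-week background assumption does not fit a schedule whose last serum is at week 12

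*Protocol*

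**What the plan says.** **Arms.** The project summary, the Overview of study (Part 2) and Sample size considerations give four infant groups: 136 on two doses of 10^5 ffu, 136 on three doses of 10^5, 136 on two doses of 10^6, and 68 on placebo. The Overview heads this part double-blind and describes the administrations as "Two/three doses of vaccine or placebo, 4 weeks apart". The Budget justification speaks of "either one or two or three doses of vaccination to about 566 healthy children", toddlers and infants together. Neither gives the number of administrations in the placebo group.

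**Schedule.** The Outline of study procedures for infants is one list for all: administrations on Days 0, 28 and 56, and blood on Days 0, 28, 56 and 84. The Day 56 entry reads "Prepare study vaccine and administer dose 3". The follow-up entry is headed "Day 85 to 6 months after third dose". There is no separate path for a 2-dose or placebo infant.

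**Serum and endpoint.** The Outline of the study says "Serum specimens will be collected at each study visit and 4 weeks after the last dose from all subjects only in part 2". The Part 2 primary aim is immunogenicity after any dose. The expected outcomes and Data Analysis sections name the four-fold rise and the geometric mean titre (GMT), without a day.

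**Background.** Sample size considerations assume that "35% of infants will be exposed to wild type rotavirus during the 8 week study period".

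**The concern.** Two things do not fit together.

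First, the arm definitions and the visit schedule describe different treatment for 272 infants. Followed literally, the schedule leaves no 2-dose arm, and so no comparison of two with three doses, which the Background gives as a purpose of the study. What each infant receives at a visit is protocol content and cannot be left to an analysis plan.

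Second, the background rate is tied to 8 weeks, while the last scheduled serum is at week 12. Eight weeks ends at Day 56, which is 4 weeks after a second dose. The sample size text therefore appears to describe a 2-dose study and the schedule a 3-dose study.

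These combine on the read time. The only post-vaccination anchor is relative to the last dose. If the last dose falls on different days in different arms, arms could be compared after different lengths of wild-type exposure. At the assumed 35% in 8 weeks, four more weeks is not negligible.

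**Working it through.** **1. The plan's own figure.** Inputs: 70% v 85% take and 136 per vaccine arm (Sample size considerations). Alpha 0.05 and power 80% are stated only for the Part 1 fever calculation; I assume that they carry over and that the test is two-sided.

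n = [1.96·√(2·0.775·0.225) + 0.842·√(0.70·0.30 + 0.85·0.15)]² / 0.15² = 121 per arm, or 134 with continuity correction. This reproduces 136 to within 2.

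**2. Exposure at the last serum.** Input: 35% in 8 weeks.
- Constant hazard: 1 − 0.65^(12/8) = 47.6% at 12 weeks.
- Linear: 0.35 × 12/8 = 52.5%.

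**3. Vaccine arm v placebo at Day 84 (136 v 68).** Power = Φ[(d − 1.96·SE0)/SE1], where SE0 is the pooled and SE1 the unpooled standard error. Observed vaccine take is held at 70%, and every exposure is taken to give a four-fold rise.

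| Placebo | d | SE0 | SE1 | Power |
|---|---|---|---|---|
| 35% (week 8) | 0.350 | 0.0732 | 0.0699 | 99.8% |
| 47.6% (week 12) | 0.224 | 0.0719 | 0.0722 | 87.5% |
| 52.5% (week 12) | 0.175 | 0.0712 | 0.0722 | 68.8% |

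Holding 70% fixed matters. If 70% is the take at week 8 and exposure raises the vaccine arm too, as in step 4, the comparisons become 75.8% v 47.6% and 78.1% v 52.5%. The same formula then gives 97.9% and 95.9%.

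**4. Two v three doses, only if read at week 8 v week 12.** Assume equal vaccine-specific take v in both arms, independent of exposure. Then take at week 8 is p8 = 1 − (1 − v)(0.65), so v = 1 − (1 − p8)/0.65. Take at week 12 is 1 − (1 − v)(1 − exposure).

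| p8 | v | Week 12, constant hazard | Week 12, linear |
|---|---|---|---|
| 70% | 53.8% | 75.8% (+5.8) | 78.1% (+8.1) |
| 75% | 61.5% | 79.8% (+4.8) | 81.7% (+6.7) |
| 85% | 76.9% | 87.9% (+2.9) | 89.0% (+4.0) |

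With 136 per arm and constant hazard, a two-sided 5% test would reject equal vaccine effect 18.9%, 15.7% and 10.4% of the time in these three rows.

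The shift shrinks with the background. At 10% over 8 weeks, 12-week exposure is 1 − 0.9^1.5 = 14.6%, and 75% becomes 1 − (0.25/0.90)(0.854) = 76.3%, or +1.3 points. It also shrinks if some exposures give no four-fold rise.

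**5. Does the budget settle Day 56?** The rotavirus test line counts 2,430. Five stools per dose over three doses is 15 per infant in the shedding subset; 150 × 15 + 90 toddlers × 2 = 2,430. This matches three administrations for the whole subset, whatever the arm. It is an inference from a cost line and does not state what is given.

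**The case against.** A reader might infer that the endpoint is set 4 weeks after the last dose, so that arms are read at 8 or 12 weeks. The documents do not say this. The sentence is a sampling rule, it also requires serum at each study visit, and all infants are bled on Days 56 and 84. A common read is available either way, and no arm has an extra bleed.

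A reader might also infer that the blind is broken. A single unbranched list is what a blinded schedule normally looks like. The same wording about preparing study vaccine is used for toddlers, a third of whom receive placebo, and the Outline of the study says that infants receive vaccine or placebo by a randomisation list. Dose 3 can therefore mean the allocated blinded product. The stool count points to three administrations for all, in which case 4 weeks after the last dose is Day 84 in every arm. Unblinding and unequal read times arise only if some infants receive nothing on Day 56.

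The most alarming figure is also conditional. An inert vaccine read at Day 84 against placebo read at Day 56 would gain 47.6 − 35 = 12.6 points and be declared different about 40% of the time. No passage pairs the arms in that way. Nor can the step 4 shift be set against the planned 12-point difference (75% v 87%), which concerns 10^5 v 10^6 at two doses on a shared schedule.

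Finally, a read day is commonly left to an analysis plan. On its own it would not be a finding.

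All of this stands, and it limits the point. It does not remove the missing Day 56 instruction or the 8-week assumption attached to a 12-week schedule.

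**Conclusion.** The point holds as a contradiction and a mismatched planning assumption. It is not a demonstrated bias or a demonstrated break of the blind.

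- **Certain from the text:** two 2-dose arms and a placebo arm have no stated Day 56 procedure, and the only schedule lists dose 3 for all infants and anchors follow-up to it.
- **Follows from the protocol's own 35%:** background by Day 84 is about 48% to 52.5%. Power against placebo for an observed 70% take falls from 99.8% to 87.5% or 68.8%. The loss is small (97.9% or 95.9%) if the vaccine arm's take rises with exposure too.
- **Conditional:** a false 3 to 8 points in favour of three doses over two, only if 2-dose infants have their last administration on Day 28 and each arm is read 4 weeks after its last dose. This also assumes independence and a four-fold rise after every exposure.
- **Not affected:** two doses of 10^5 v two doses of 10^6.

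**What to change.** 1. Reconcile the Overview of study (Part 2), the serum rule in the Outline of the study, and the Day 56 and follow-up entries of the infant procedures. State what each arm, including placebo, receives at each visit, consistently with the double-blind design. Which procedure is right is for the sponsor and investigators to decide.
2. Name read days by study day: Day 56 in all arms for take after two doses, and Day 84 in all arms for three v two doses and three doses v placebo. The Day 56 read presumes that the two doses are those on Days 0 and 28, which item 1 should confirm.
3. Restate the background for each read day: 35% by Day 56, and about 48% (constant hazard) to 52.5% (linear) by Day 84, with the assumption and range written down and power against placebo recomputed.

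**Cost.** Protocol wording only. Serum is already scheduled for all infants on both days. The assay count should be checked, because the IgA budget line does not agree with itself (4X3X525 beside 4, 4 and 576).

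**Downside to state.** If the 2-dose arms have their active doses on Days 0 and 28, then at Day 84 they are 8 weeks from the last active dose and the 3-dose arm is 4 weeks. This matters mainly for GMT.
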